1.0 SCHEMA

- Title:** Swaziland HIV Incidence Measurement Survey (SHIMS)
- Short Title:** HIV Incidence in Swaziland
- Protocol Co-Chairs:** [name], [name], [name], and [name]
- Background:** The Government of the Kingdom of Swaziland plans to scale-up HIV prevention, care and treatment public health programs over a twelve-month period, including the Male Circumcision Accelerated Saturation Initiative (MC ASI) campaign. The MC ASI *program* will track the number of MC procedures but will not evaluate the impact of the campaign on the HIV epidemic. This research study will neither provide nor promote male circumcision services.
- Purpose:** To determine HIV incidence at a population level before and after the independent public health program--Male Circumcision Accelerated Saturation Initiative (MC ASI)—and concurrent with the expansion of other HIV prevention, care and treatment programs in Swaziland
- Design/
Duration:** Two separate cross-sectional household surveys, one before and one after MC ASI, in order to identify three prospective, longitudinal observational cohorts
- Two independent separate short term cohorts representative samples of HIV-uninfected adult men and women before and after completion of the MC ASI. (Cohort “A1” before ASI, and “A2” after ASI). Cohort A1 is followed for 6 months; Cohort A2 is followed for 12 months.
- One long-term cohort (Cohort “B”) comprised of a subset of the highest risk age groups of men and women from Cohort A2. Cohort B is followed for an additional 6-18 months (beyond the 12 months of Cohort A2).
- One cross-sectional observational survey (Cross-Sectional Cohort “C”) comprised of a subset of HIV-infected men and women who participated in Pre-Cohort A1. Cohort C participants are visited approximately 6 to 12 months after the initial A1 visit.
- Sample Size:** A total of approximately 34,421 individuals from a sample of approximately 30,645 households over a 3 1/2-year period will be included in the study. Of the 34,421, a subset of 26,618 individuals

will participate in either Cohort A1, Cohort A2, or in A2 and B, as follows:

- 1) Two cross-sectional household surveys: 14,884 households for A1 and 15,758 households for A2.
- 2) Two separate, nationally representative, HIV-uninfected longitudinal cohorts of 5,823 men and 7,106 women (Cohort A1) and 6,165 men and 7,524 women (Cohort A2)

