7.2 Sampling, including sample size and statistical power

A nationally-representative sample of men and women will be identified for both the baseline and post-intervention surveys and cohorts via a two-stage cluster-based sampling of 'enumeration areas' and households. Enumeration areas are sampling points defined by the 2007 Swaziland Population and Housing Census. A total of approximately 575 enumerations areas will be drawn from the census sample frame of all 2000 enumeration areas with a probability of selection proportional to the number of households within the enumeration area. The enumeration areas in urban versus rural areas will be proportional to the urban versus rural distribution of the population. Between November 2010 and May 2011, staff will conduct an exhaustive listing of households within each sampled enumeration area. During household listing, study staff will use Global Positioning Systems (GPS) receiver to record the geographic coordinates of each cluster and household. In the pre-MCASI cohort, approximately 14,884 households will be sampled, and 12,301 households will participate in the study. From these households we expect to identify, recruit, screen, and enroll a sample size of 5,823 men and approximately 7,106 women in the first seroincidence cohort (Cohort A1). In the post-MC ASI cohort, approximately 15,758 households will be sampled, and 13,024 households will participate in the study. From these households we expect to identify, recruit, screen, and enroll a sample size of 6,165 men and approximately 7,524 women in the second seroincidence cohort (Cohort A2). From Cohort A2, we expect approximately 25% of the men will be 25-34 years old, and 29% of the women will be 18-24 years old, yielding the longer, 6 month longitudinal cohorts of 1,541 men and 2,182 women (Cohort B).

Statistical power calculations for primary objectives are included as Appendix P.

Primary Objective #1a:

To estimate HIV incidence in household-based representative sample of men at baseline and post MC ASI. (Cohort A1 vs A2)

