 - 13% will be vacant/non-contactable, 5% will refuse participation at the household level. Adjustment factor = $1/0.87 \times 0.95 = 1.21$
- Household individual adjustment
 - Men: 92% will have male residents within the eligible age range, 77% of men will be HIV uninfected, 99% will agree to cohort enrollment, 90% will be contactable, 95% will agree to pre-cohort survey. Adjustment factor = $1/(0.92 \times 0.77 \times 0.99 \times 0.90 \times 0.95) = 2.11$
- Loss to follow-up
 - Men: 90% and 85% of men will complete follow-up in the 6 and 12 month cohorts, respectively (accounting for loss-to-follow-up, interview/HIV test refusal at follow-up, data loss, and specimen loss totaling 10% and 15%, respectively). Lost to follow-up adjustment = 1.11 and 1.18

Table 2: Number of enrolled male participants, participating households and households in sample required to achieve the targeted effective number of person years.

Effective number person years	Design effect	Loss to follow-up adjustment	Number Males enrolled	Male household adjustment	Number of households participate	Household adjustment	Number of households sampled
Pre-MC ASI Male Seroincidence Cohort (Cohort A1) – 6 month follow-up period							
2096	1.25	1.11	5823	2.11	12301	1.21	14884
Post-MC ASI Male Seroincidence Cohort (Cohort A2) – 12 month follow-up period							
4192	1.25	1.18	6165	2.11	13023	1.21	15758

The decision to power the evaluation to detect a 45% reduction in incidence in men is based upon a combination of factors: 1) mathematical modeling estimations of HIV incidence reduction anticipated in men following MC scale-up to 80% coverage in 2011; and 2) meta-analyses of efficacy results from the 3 MC RCTs (See Figure 2). The proportional hazard risk ratio (efficacy) from the 2009 Cochrane Review meta-analysis using case analyses from the three MC RCTs was 0.46 (95% CI, 0.34 – 0.62), which equates to a 54% risk reduction against HIV acquisition [Sigfried, 2009].

Primary Objective #1b:

To estimate HIV incidence in household-based representative sample of women at baseline and post MC ASI (Cohort A1 vs A2)

Mathematical modeling estimation of HIV incidence reduction anticipated in women following MC scale-up to 80% coverage in 2011 is expected to produce less than a 45% reduction in women (See Figure 1). Newly diagnosing approximately 35,000 men and

enrolled approximately 4,500 on ART may also contribute to reductions in HIV incidence.

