The household sample of 14,884 and 15,758 in pre- and post- MC-ASI is expected to yield an enrolled cohort of 7106 women and 7,524 in the pre- and post-MC ASI cohorts respectively. (See Table 3)

Number of effective women-years accumulated-

The number of effective women years accumulated from the household sample of 14,884 and 15,758 in pre- and post- MS-ASI is shown in Table 3. The derivation of each of the adjustment factors is as follows:

- Design Effect: Design effect for HIV in women ages 15-49 of 1.25, and the DEFT of 1.32, are both based on the 2006-07 DHS.
- Household adjustment
 - 13% will be vacant/non-contactable, 5% will refuse participation at the household level. Adjustment factor = $1/0.87 \times 0.95 = 1.21$
- Household individual adjustment
 - Women: 105% will have female residents within the eligible age range, 65% will be HIV uninfected, 99% will agree to cohort enrollment, 90% will be contactable, 95% will agree to pre-cohort survey. Adjustment factor = $1/(1.05 \times 0.65 \times 0.99 \times 0.90 \times 0.95) = 1.73$
- Loss to follow-up

Women: 92% and 88% of women will complete follow-up in the 6 and 12 month cohorts, respectively (accounting for loss-to-follow-up, interview/HIV test refusal, data loss, and specimen loss totaling 8% and 12%, respectively). Adjustment factor = $1/0.92 = 1.09$ and $1/0.88 = 1.14$ respectively.

Table 3: Number of enrolled female participants, given sample of 14,884 and 15,758 households in the pre- and post-MC ASI cohort.

Effective number person years	Design effect	Loss to follow-up adjustment	Number Females enrolled	Female household adjustment	Number of households participating	Household adjustment	Number of households sampled
Pre-MC ASIFemale Seroincidence Cohort (Cohort A1) – 6 month follow-up period							
2615	1.25	1.09	7106	1.73	12,301	1.21	14884
Post-MC ASIFemale Seroincidence Cohort (Cohort A2) – 12 month follow-up period							
5297	1.25	1.14	7524	1.73	13,023	1.21	15758

With total effective person years of 7912 in the women, assuming a seroincidence rate of 3.0 per 100 person years, and a sample ratio of 1:2, we have 68% power to detect a 30% reduction in HIV seroincidence and 82% power to detect a 35% reduction in HIV seroincidence.

Primary Objective #2a

To estimate HIV incidence rates in the highest risk age subsets of men ages 25-34 in the household-based, nationally representative sample for an additional 6-18 months after the MC ASI completion (Cohort B).

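### The five male rates printed in section 7.2 give a household adjustment factor of 1.67, not the 2.11 from which Table 2 derives the household sample

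*Protocol*

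**What the plan says.** The derivation of the household sample is in Protocol section 7.2, under Primary Objective 1a and Table 2. For men it lists an eligible-resident figure ("92% will have male residents within the eligible age range"), an HIV-negative proportion ("77% of men will be HIV uninfected"), and three participation rates ("99% will agree to cohort enrollment, 90% will be contactable, 95% will agree to pre-cohort survey"). It then prints the result: "Adjustment factor = $1/(0.92 \times 0.77 \times 0.99 \times 0.90 \times 0.95) = 2.11".

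Table 2 multiplies 5,823 men (Cohort A1) and 6,165 men (Cohort A2) by this factor to obtain 12,301 and 13,023 participating households, and by 1.21 to obtain the households to be sampled. The text of section 7.2 repeats the A1 figures: "In the pre-MCASI cohort, approximately 14,884 households will be sampled, and 12,301 households will participate in the study".

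For women, under Primary Objective 1b, the same three participation rates are used and the factor is "Adjustment factor = $1/(1.05 \times 0.65 \times 0.99 \times 0.90 \times 0.95) = 1.73". Table 3 takes the household counts from the men's calculation as given and derives 7,106 and 7,524 women from them, with stated power of 68% for a 30% reduction and 82% for a 35% reduction.

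The schema (section 1.0) gives the overall size: "A total of approximately 34,421 individuals from a sample of approximately 30,645 households". Of these, 26,618 are to enter the cohorts.

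**The concern.** The factor is written as an explicit product, so it can be checked on the page, and it fails. It is also the only link between the number of men required and the number of households to visit. The resulting 14,884 and 15,758 households appear in the schema, section 5.1, section 7.2 and Table 3, where they fix the size and power of the women's cohort.

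At stake is whether the plan's expected male participation and its field sample describe the same study. Either the expected male yield is understated, or at least one of the printed male rates is too favourable. Section 8.1.1 lets the Principal Investigators adjust sample sizes, and they would need a sound derivation to do so.

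**Working it through.** **Inputs** (all Protocol section 7.2 unless noted). Men: 0.92, 0.77, 0.99, 0.90, 0.95. Women: 1.05, 0.65, 0.99, 0.90, 0.95. Household factor 1.21. Design effect 1.25. Men completing follow-up 90% (A1) and 85% (A2); women 92% and 88%. Men's rates 2.0 versus 1.1 per 100 person-years. Women's baseline rate 3.0 per 100 person-years.

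**1. The surrounding figures reproduce.**
- Person-years by the Wald formula at a 1:2 ratio, two-sided 0.05 and 80% power: 6,289 (text 6,288, Table 1 6,289).
- Men enrolled: 2,096 × 1.25 / 0.90 / 0.5 = 5,822 and 4,192 × 1.25 / 0.85 = 6,165 (stated 5,823 and 6,165).
- Household factor: 1/(0.87 × 0.95) = 1.21.
- Women's factor: 1/0.5777 = 1.731 (stated 1.73).

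**2. The men's factor does not.** 0.92 × 0.77 × 0.99 × 0.90 × 0.95 = 0.5996, and 1/0.5996 = 1.668. The stated 2.11 is about 27% higher (2.11/1.668 = 1.265). Multiplying 1.668 by another factor in the plan does not give 2.11 either: × 1.25 = 2.08; × 1.21 = 2.02; × 1.11 = 1.85; × 1.18 = 1.97.

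**3. Table 2 uses the stated factor.** 12,301/5,823 = 2.1125 and 13,023/6,165 = 2.1124.

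**4. Which rate change would give about 2.11?** Changing one rate at a time: 0.95 to 0.75, 0.90 to about 0.71, 0.99 to about 0.78, 0.77 to about 0.61, or 0.92 to about 0.727. With 0.75 in place of 0.95 the factor is 2.1124, and 5,823 × 2.1124 = 12,301 and 6,165 × 2.1124 = 13,023, both exact.

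**5. If the listed rates are right and the households are kept.**
- Men: 12,301/1.6677 = 7,376 and 13,023/1.6677 = 7,809, together 15,185.
- Cohort total: 15,185 + 7,106 + 7,524 = 29,815, against 26,618.
- Effective male person-years: 7,376 × 0.5 × 0.90 / 1.25 = 2,655 and 7,809 × 0.85 / 1.25 = 5,310.
- Power = Φ(|ln 0.55| / √(1/(2,655 × 0.020) + 1/(5,310 × 0.011)) − 1.96) = Φ(0.598/0.1896 − 1.96) = Φ(1.19) = 88%. The same formula with 2,096 and 4,192 returns the planned 80%.

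**6. If the households were instead cut to fit 1.67.**
- Participating: 5,823 × 1.6677 = 9,711 and 6,165 × 1.6677 = 10,281. Sampled: about 11,750 and 12,440.
- Women: 9,711/1.731 = 5,610 and 10,281/1.731 = 5,940.
- Effective female person-years: 5,610 × 0.5 × 0.92 / 1.25 = 2,065 and 5,940 × 0.88 / 1.25 = about 4,181, together about 6,246 against the stated 7,912.
- Women's power by the same formula: about 58% for a 30% reduction and about 72% for a 35% reduction. With Table 3's 2,615 and 5,297 it returns the stated 68% and 82%.

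**7. The schema totals.**
- Survey participants implied by stated enrolment: men (5,823 + 6,165)/(0.77 × 0.99) = 15,726; women (7,106 + 7,524)/(0.65 × 0.99) = 22,735; together 38,461.
- Listed rates applied to the stated 25,324 participating households: men 25,324 × 0.92 × 0.90 × 0.95 = 19,920; women 25,324 × 1.05 × 0.90 × 0.95 = 22,735; together about 42,650.
- Neither is near 34,421.
- Households: 14,884 + 15,758 = 30,642 against about 30,645, a trivial difference.

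**The case against.** The strongest reply is that nothing the trial depends on is put at risk. The 5,823 and 6,165 men follow from person-years, design effect and loss to follow-up, all of which reproduce. Given 2.11, the households, the men and the 26,618 agree with one another. If the printed rates are right, the study enrols more men than it needs; if 2.11 is right, one printed rate is a slip and every household count stands. All of that is correct, and it confines the point to a conflict between the five listed rates and the factor actually used.

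Three stronger readings are tempting but not supported.

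- A reader might infer that the study could visit about 6,452 fewer households (21%). Those households suffice only for Objective 1a. They also supply the women for primary Objective 1b, whose power would fall as shown in step 6.
- A reader might conclude that male survey agreement was really planned at 75%, because that reproduces Table 2 to the unit. It is a plausible misprint, but other rate changes give about 2.11 too, and the document does not say which figure is wrong.
- A reader might attribute the 34,421 to the same error. The 38,461 back-calculation does not use the men's factor at all, and neither factor yields 34,421, so it is a separate discrepancy. The plan calls the figure approximate and shows no derivation, but the gap to 38,461 is about 12% of the stated total, more than rounding explains.

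**Conclusion.** The point holds in this limited form. The male rates printed in section 7.2 give 1.67, Table 2 uses about 2.11, and the two cannot both be right. The fault is confined to the men's line; the women's factor, the person-years and the enrolment targets all reproduce.

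If the listed rates are right, the expected men are understated by about 3,200 (15,185 against 11,988) and Objective 1a would have about 88% power. If 2.11 is right, the product of the five male rates is about 0.474 rather than 0.600, and the expected male yield per household is lower than the printed rates imply. Objective 1a's planned 80% power is not threatened in either case, provided that the enrolment targets are met. The 88% rests on the plan's own design effect, follow-up and incidence assumptions.

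The schema total of 34,421 is a second, independent discrepancy.

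**What to change.** Reconcile the men's rates with the factor in section 7.2, in one of two ways.

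(a) If 2.11 was intended, correct whichever printed male rate is wrong, in both the prose and the formula. All household counts then stand, and the change is one line.

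(b) If the listed rates are right, correct the factor to 1.67 and keep 14,884 and 15,758 households, because they carry the women's stated 68% and 82% power. Restate the expected men as about 7,376 (A1) and 7,809 (A2), and Objective 1a power as about 88%, in Table 2 and sections 1.0 and 7.2, and the 26,618 as about 29,815. Figures built on the male counts move with them. For example, the 25% share aged 25-34 becomes about 1,844 in A1 and 1,952 in A2, against 1,456 and 1,541; the power statements for Objectives 2a and 3 should be rechecked.

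In either case, recompute the schema's 34,421 and show its derivation: about 38,460 from the stated enrolment under (a), about 42,650 under (b). Under (a) the figure assumes that the HIV-negative and cohort-agreement rates are not the ones corrected.

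The cost is editorial under (a). Under (b), the larger male cohort means more follow-up visits and HIV tests than are now budgeted, unless the plan caps male enrolment.

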5.2.1 HIV status

During each contact with participants, consenting adults will be tested for HIV for this study using a serial algorithm for rapid tests approved by the Swaziland National Reference Laboratory. This algorithm includes the use of the 4th generation Determine rapid test kits that are capable of detecting HIV antigens. Samples from persons that are

HIV antigen reactive will subsequently be tested using both enzyme immunoassay (EIA) and nucleic acid detection tests (NAT) in the laboratory (Appendix A). NAT are HIV-discriminatory assays approved by the FDA to detect HIV-1 protein/antigens, which are produced by the body prior to the production of antibodies. NAT will be used in this protocol to identify people who were very recently HIV-infected who might not have had their HIV infection detected if only rapid HIV tests that detect antibodies were being used. The use of HIV antigen detection tests is to avoid enrollment of acutely HIV-infected individuals into the cohorts.

1. Confirmed HIV-negative: Negative per the serial algorithm for rapid HIV testing that includes 4th generation Determine, approved for this study. See Appendix A.
2. Confirmed HIV-positive: Positive per the serial algorithm for rapid HIV testing that includes 4th generation Determine, approved for this study. See Appendix A.

Sub-categories defining duration of HIV infection among confirmed HIV-positive persons are as follows:

- HIV-positive Incident Infection: identified by direct observation of HIV seroconversion during the period of participation in the cohort, i.e. a person was confirmed HIV-negative at cohort enrollment and confirmed HIV-positive at cohort follow-up.
 - HIV-positive Non-recent/Prevalent Infection: identified as HIV-positive as part of the pre-cohort survey based upon the serial algorithm for rapid testing approved for this study. See Appendix A.
3. HIV indeterminate: Indeterminate per the serial algorithm for rapid HIV testing that includes 4th generation Determine, approved for this study. See Appendix A.

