6.2.4 Follow-up Visits

Cohort A1 and A2 participants will be visited again at their place of residence for a follow-up visit at 6 months (Cohort A1) or 12 months (Cohort A2) after enrollment.

For each follow-up appointment at the home, at least 3 attempts will be made by study staff to establish contact in person and complete the follow-up visit activities. Visits will

ideally be completed within a specified ± 14 day window around target follow-up dates. The allowable follow-up dates, however, will extend to the date of study conclusion. Detailed information regarding visit windows will be thoroughly described in the SHIMS SOP on retention. The following procedures/assessments are to be performed at the cohort follow-up study visits:

- Verification of the participant's identity and participation in the study
- Selection of a relatively private location either inside or outside the participant's home, so that the follow-up visit may take place with as much privacy as possible, as appropriate review of the study goals and procedures
- For men, an interviewer-administered questionnaire to detect changes in self-reported MC status
- Participants who were uncircumcised at cohort enrollment but circumcised at cohort follow-up will be asked to provide information about the date and location of the MC surgery (Appendix K). Their medical records related to their MC surgery will be abstracted at the facility that performed the MC surgery to determine the date of surgery.
- Blood draw of approximately 7-10mL
 - HIV testing and counseling using the serial algorithm for rapid HIV testing that is approved for this study (Appendix A).
 - See procedures outlined in Section 6.1.2.1-6.1.2.3 for instructions on handling HIV test results.

Those who decline cohort follow-up will be thanked for their time and asked to provide basic information about their reason for refusal to assist in characterizing the impact of refusal on study outcomes. This information will be documented in the appropriate section of the Short/Long-term Cohort Follow-up CRF(s) (Appendices K-N).

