6.2.4.1 Additional Study procedures for participants who test HIV-positive at the follow-up visit

- Interviewer administered questions to assess whether the participant has previously tested HIV-positive and whether HIV care and treatment has been sought.
- Counseling about the benefits of HIV care and treatment services and provision of information to help them link to these services.
- Counseling regarding importance of HIV testing of partners and referral to HIV testing sites.
- Male participants identified as newly circumcised **and** newly HIV-infected at follow-up (were uncircumcised at cohort enrollment) will be asked to provide information about the date and location of the MC surgery, whether they had an HIV test the day of the MC surgery, and the HIV test result, to help determine HIV status at the time of circumcision. Their medical records related to their MC surgery will be abstracted at the facility that performed the MC surgery to determine whether an HIV test was conducted pre-operatively and the results of the test, if done.

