The sample size for the men’s Cohort A1 is 5,823 and for Cohort A2 is 6,165. Each person enrolled in Cohort A1 contributes 6 months of follow-up and in Cohort A2, each contributes 12 months of follow-up. The sample size is chosen to achieve sufficient “effective” person years to achieve 80% power to detect a 45% reduction in ratio of infection rates, assuming a Poisson distribution in each cohort of number of seroconversion events in total accumulated person years.

Note: Very similar sample sizes result from comparison of binomial probabilities of the proportion of the cohort infected in the pre vs. post MC ASI cohorts, provided exact methods are used. Poisson analysis is planned to accommodate varying lengths of follow-up time in the follow-up cohort.

- Men. The total number of person-years required to detect a 45% reduction in the HIV incidence rate from 2.0 per 100 person years (approximated baseline rate) to 1.1 per 100 person years (post-intervention) with a 1:2 ratio of person years in the two cohorts is 6,288. With a design effect of 1.25 and loss to follow-up of 10% and 15% in the pre- and post-MC ASI this yields a sample size of 5,823 men followed for 6 months and 6,165 men followed for 12 months in Cohort A1 and Cohort A2 respectively. (See Tables 1 and 2)

Table 1:

Effective person years required to detect 30-60% difference between infection rates with 6 month follow-up in Cohort A1, 12 month follow-up in Cohort A2, for two sided alpha of 0.05, and 80% power. Wald test statistic for slope in Poisson Regression, under assumption of simple random sample.				
λ_1	λ_2	Ratio λ_2/λ_1	Total Effective ¹ Person Years (Both serocohorts combined)	
0.0200	0.0140	0.70	15865	
0.0200	0.0130	0.65	11224	
0.0200	0.0120	0.60	8272	
0.0200	0.0110	0.55	6289	
0.0200	0.0100	0.50	4901	
0.0200	0.0090	0.45	3898	
0.0200	0.0080	0.40	3155	
0.0300	0.0210	0.70	10577	
0.0300	0.0195	0.65	7483	
0.0300	0.0180	0.60	5514	
0.0300	0.0165	0.55	4192	
0.0300	0.0150	0.50	3267	
0.0300	0.0135	0.45	2599	
0.0300	0.0120	0.40	2103	

¹Effective person years assume a simple random sample.

Number of households

The number of households required to achieve the effective sample size is shown in Table 2. The derivation of each of the adjustment factors is as follows:

- Design Effect: Design effect for HIV in men ages 15-49 of 1.25, and the DEFT of 1.32, are both based on the 2006-07 DHS.
- Household adjustment:

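### A cohort member diagnosed elsewhere who declines the follow-up test is lost as non-response, and with 6- versus 12-month intervals this can bias the A2/A1 rate ratio toward a decline

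*Protocol*

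**What the plan says.** Four provisions of the protocol act together.

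- **Case definition (5.2.1).** An incident infection means that "a person was confirmed HIV-negative at cohort enrollment and confirmed HIV-positive at cohort follow-up", by the study's own algorithm. No rule lets a diagnosis made elsewhere count.
- **Decliners (6.2.4, similarly 6.3.4).** "Those who decline cohort follow-up will be thanked for their time and asked to provide basic information about their reason for refusal". Nothing else is listed for them.
- **Earlier positive test (6.2.4.1, repeated for Cohort B in 6.3.4.1).** "Interviewer administered questions to assess whether the participant has previously tested HIV-positive and whether HIV care and treatment has been sought" is listed as a procedure for people who test positive at the visit.
- **Loss (7.2, 7.3).** The sample-size text for men places test refusal in one allowance with the other losses: "accounting for loss-to-follow-up, interview/HIV test refusal at follow-up, data loss, and specimen loss totaling 10% and 15" percent in A1 and A2. The allowance for women is built in the same way. Section 7.3 handles loss to follow-up through the non-response weights. It spells this out for the 6-month follow-up, and I assume that the same applies to A2.

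The sensitivity analyses in 8.1.3 cover household clustering and demographic change. Section 8.9 discusses selective loss only in terms of migration and answers it with sample size, which protects power but does not remove bias.

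**The concern.** Someone who has learned of an infection between the two study visits may see little reason to be tested again. If that person declines, the refusal is a consequence of the outcome. Non-response weights give the decliner the risk of tested people with similar recorded characteristics, whereas the true outcome is a known infection. The case is lost, and the incidence estimate for that cohort is too low.

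The primary comparison sets a 6-month interval against a 12-month interval. A longer interval leaves more time for an infection to be diagnosed elsewhere before the visit. Other things being equal, a larger share of cases would be lost from A2 than from A1, which pulls the ratio toward the decline that the study hypothesises (2.6). The gap lies in data collection and case definition, so a later analysis plan could not recover answers that were never sought.

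**Working it through.** **The plan's own figure first.** The inputs in 7.2 are "for two sided alpha of 0.05, and 80% power" and rates "from 2.0 per 100 person years (approximated baseline rate) to 1.1 per 100 person years (post-intervention) with a 1:2 ratio of person years". For the Wald test on the log rate ratio, A1 needs

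(1.960 + 0.842)² × (1/0.020 + 1/(2 × 0.011)) / (ln 0.55)² = 2,096 effective person-years,

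and the total is 3 × 2,096.2 = 6,289, as in Table 1 (the text has 6,288). "With a design effect of 1.25 and loss to follow-up of 10% and 15% in the pre- and post-MC ASI" then gives 2,096 × 1.25 / 0.90 / 0.5 = 5,822 men (stated 5,823) and 4,192 × 1.25 / 0.85 = 6,165 men (as stated). The sample size reproduces, so the point is not one of arithmetic.

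**Expected cases among men who complete follow-up.**
- A1: 5,823 × 0.90 × 0.5 = 2,620 person-years; × 0.020 = 52 cases.
- A2: 6,165 × 0.85 × 1 = 5,240 person-years; × 0.011 = 58 cases, or 105 if the rate stays at 0.020.

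**Model for the lost cases.** Infection time is uniform over the interval T. After infection, diagnosis elsewhere occurs at rate d per year. A person so diagnosed declines the study test with probability q. Then

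- share diagnosed by the visit: f(T) = 1 − (1 − e^(−dT)) / (dT);
- share of cases missed: q × f(T);
- factor on the A2/A1 ratio: (1 − q f(1)) / (1 − q f(0.5)).

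Cases are a small fraction of each cohort, so the effect on person-years is ignored. The documents give neither d nor q. I assume d from 0.1 to 0.8 per year and q from 25% to 100%, equal in the two cohorts.

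| d | q | Missed A1 | Missed A2 | Factor | True 0.55 reads as |
|---|---|---|---|---|---|
| 0.1 | 0.25 | 0.6% | 1.2% | 0.994 | 0.547 |
| 0.3 | 0.50 | 3.6% | 6.8% | 0.966 | 0.532 |
| 0.5 | 0.50 | 5.8% | 10.7% | 0.948 | 0.521 |
| 0.8 | 1.00 | 17.6% | 31.2% | 0.835 | 0.459 |

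For example, with d = 0.3: f(0.5) = 0.071, f(1) = 0.136, and (1 − 0.068) / (1 − 0.036) = 0.966. In cases, this is about 1.9 missed in A1 and 3.9 in A2 (7.1 in A2 if there is no true reduction).

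**When the direction changes.** f depends only on d × T. With the same q, the factor is 1 exactly when the diagnosis rate in A1 is twice that in A2, and above 1 beyond that. With d = 0.5 in A1, 0.1 in A2 and q = 0.5, it is (1 − 0.024) / (1 − 0.058) = 1.035. With d = 0.1 in A1, 0.3 in A2 and q = 0.5, it is 0.944.

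**Effect on the test.** With no true change and 2,096 and 4,192 effective person-years, the two-sided 5% error rate becomes about 5.5% for a factor of 0.96, 8.5% for 0.90 and 13.3% for 0.85.

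**The case against.** **Some disclosures may be captured.** Section 6.5.2 provides for the date of diagnosis to be recorded for people who report having known of their infection before study testing, and does not confine this to those who test positive at the visit. Appendix K lists a section on HIV testing history. A decliner may give a known diagnosis as the reason for refusing, the Termination Form records why follow-up was not completed (6.6.3), and those lost are to be described (8.1.2). This stands, and it means that refusal can already largely be separated from failure to locate. It does not close the gap: a person who declines the whole visit may never be asked, and 5.2.1 would not count the answer.

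**People who know their status may still test.** Section 6.2.4.1 expects some previously diagnosed members to attend and be tested, and the follow-up allowance in 9.3.3 favours attendance. This also stands. It is a reason to consider small values of q, which nobody can fix from the documents.

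**Stronger readings.** A reader might infer three things that the documents do not support.
- *That the 10% and 15% allowance shows the effect.* It is a planning figure that pools all causes. Per unit time the assumed loss is higher in A1: 1 − 0.90² = 19% a year against 15%.
- *That testing before circumcision makes more A2 infections already known.* The campaign runs from January to December 2011 (2.1), and A2 is followed from Month 24 to Month 36 (4.0), after it. A1 is the cohort that overlaps: household listing runs to May 2011 (7.2), and 8.1.3 has a rule for A1 men circumcised between visits. Campaign testing points, if anything, the other way.
- *That more cases are certain to be lost from A2.* This is an inference from the unequal intervals. It needs similar diagnosis and refusal rates in the two cohorts, or higher ones in A2.

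**The analysis plan.** A further sensitivity analysis is often left to it. The question to decliners cannot be.

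**Conclusion.** The point holds in conditional form. Under 5.2.1, 6.2.4 and 7.3, an infection diagnosed elsewhere in someone who declines the follow-up test leaves the analysis as non-response, and weights on observed characteristics cannot restore it. If outside diagnosis and refusal once diagnosed are similar in A1 and A2, the missed share in A2 is about 1.8 to 2.0 times that in A1, and the rate ratio is biased toward a decline.

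The size rests wholly on assumed inputs: a factor of about 0.99 to 0.84, with about 0.95 to 0.97 in the middle scenarios. A factor of 0.966 is about 0.16 standard errors of the log rate ratio at the planned design (about 42 and 46 effective events), so in the middle of the range it would rarely change the conclusion. The direction could reverse, to about 1.03 in the case computed, if outside diagnosis was much more frequent in A1. This is a cheap improvement that would show whether the effect matters; it does not show that the primary comparison is invalid.

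**What to change.** - **Sections 6.2.4 and 6.3.4:** ask every located cohort member, including those who decline the blood test, whether they have tested HIV-positive since enrolment and when, using the existing HIV testing history section of Appendices K and N.
- **Section 8.1.3:** add a sensitivity analysis of objectives 1a and 1b that counts such reports as incident infections, dated by the reported diagnosis.

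The cost is a little extra interview and analysis work. Some decliners will not answer, and members who cannot be located stay unobserved. The reports are unconfirmed self-report, which is why this should remain a sensitivity analysis. The primary case definition, the primary analysis and the sample size are unchanged.
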